#### 10.1.3.2. Safety Analyses

The occurrence of AEs was to be compared between treatment arms. Treatment-emergent AEs (TEAEs) were to be analyzed according to the number and percentage of patients who had a

TEAE, as well as the number of TEAEs with the respective Medical Dictionary for Regulatory Activities (MedDRA) System Organ Class and Preferred Term. Additionally, the number and percentage of patients with TEAEs were to be further grouped by severity and causal relationship. The number and percentage of patients with SAEs and the number of SAEs were to be analyzed. Where AEs were grouped by severity or relationship, the maximum severity/relationship per patient and class of AE was to be considered.

#### 10.1.3.3. Interim Analysis

An interim analysis was performed after the first 30 patients treated in Phase II reached at least day 15 of the study schedule to assess the clinical benefit of the treatment using the assessed clinical parameters.

### 10.2. Phase III

#### 10.2.1. Sample Size Determination

A total of 180 patients (90 per arm) are planned to be randomized in Stage 1 and up to 180 patients (90 per arm) in Stage 2. For patients randomized in error (screening failures) and patients for whom consent is withdrawn within 48 hours after randomization, additional patients will be randomized. This results in 90% overall power to show efficacy in the final efficacy analysis. The power calculation is based on an overall 2.5% one-sided alpha and an assumed 30% 28-day mortality under Placebo and 15% 28-day mortality under IFX-1 treatment.

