### **10.2. Phase III**

#### **10.2.1. Sample Size Determination**

A total of 180 patients (90 per arm) will be randomized in Stage 1 and up to 180 patients (90 per arm) in Stage 2. This results in 90% overall power (90% probability to either show efficacy after Stage 1 or Stage 2). The power calculation is based on an overall 2.5% one-sided alpha, Pocock's approach to account for the group-sequential design, a binding futility stop if the z-statistic is 0 or lower after the first stage and an assumed 30% 28-day mortality under Placebo and 15% 28-day mortality under IFX-1 treatment.

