### Number of Patients:

**Phase II:** 30 patients (15 arm A+ 15 arm B)

**Phase III:** Total of 180 patients (approximately 90 per arm) in Stage 1 and 180 patients (approximately 90 per arm) in Stage 2 are planned. The assumed rate for randomization of additional patients, i.e. patients randomized in error (screening failures) and patients for whom consent is withdrawn within 48 hours after randomization, is 10%. The planned maximum number of patients in the study is 400, 200 patients per treatment arm. The sample size ensures 90% power to show superiority of IFX-1 for the primary endpoint of 28-day all-cause mortality. Sample size calculations were based on the assumption that IFX-1 can reduce a 30% mortality under SOC by 50% to a mortality of 15% and that at least 360 patients are evaluable for the primary endpoint for the final analysis.

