**Phase III****Efficacy:**

The primary statistical analysis will be based on all randomized patients except patients randomized in error (reason for early termination documented as “Randomized by mistake” in the eCRF) who did not get IMP treatment. For patients randomized in error (screening failures) and patients for whom consent is withdrawn within 48 hours after randomization, additional patients will be randomized.

The primary efficacy variable is 28-day mortality (proportion of patients deceased until day 28).

The planned maximum number of patients in the study is 400. Up to 200 patients are planned to be randomized to Arm A and Arm B using a 1:1 allocation ratio for the first and for the

second stage each. The sample size calculation is based on an assumed rate of about 10% for additional patient randomization. A total of 180 patients (approximately 90 per arm) in Stage 1 and up to 180 patients (approximately 90 per arm) in Stage 2 are planned to be analyzed in a combined fashion for the final efficacy analyses. This results in 90% overall power to show superiority of IFX-1. The power calculation is based on an overall 2.5% one-sided alpha and an assumed 30% 28-day mortality under Placebo and 15% 28-day mortality under IFX-1 treatment.

The interim analysis is performed after 180 patients, not counting patients being randomized in error, have been followed-up until day 28 (or died before). In case the interim analysis does not result in an early stop for futility, up to 180 additional patients are planned to be randomized in a ratio of 1:1 into Arm A and B.

The primary analysis of IFX-1 + SOC compared to SOC alone will make use of a one-sided alpha level of 2.5% and will test for superiority (lower mortality among IFX-1 treated patients). The primary statistical analysis will be based on a Cox proportional hazards regression model with outcome all-cause mortality as a censored time-to-event variable and explanatory variables randomized treatment arm (Arm B versus Arm A) and age. The primary statistical analysis will be based on all randomized patients except patients randomized in error (screening failures). For the primary analysis, all-cause mortality will be censored at day 28 for subjects who died after day 28 or who have more than 28 days follow-up alive.

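### Is the 90% power in Protocol Version 4.0 a leftover from the dropped Pocock design, and so wrong for the trial now planned?

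*Combined protocol and SAP*

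**What the plan says.** In Version 4.0, Section 10.2.1 sets the size of the two stages as "A total of 180 patients (90 per arm) are planned to be randomized in Stage 1 and up to 180 patients (90 per arm"), the latter for the second stage. It then states: "This results in 90% overall power to show efficacy in the final efficacy analysis". The inputs are given there: "The power calculation is based on an overall 2.5% one-sided alpha", with "an assumed 30% 28-day mortality under Placebo and 15% 28-day mortality under IFX-1 treatment". The synopsis gives the 90% twice. Under Statistical Methods it reads "This results in 90% overall power to show superiority of IFX-1". Under Number of Patients it reads "The sample size ensures 90% power to show superiority of IFX-1 for the primary endpoint of 28-day all-cause mortality", on the condition that "at least 360 patients are evaluable for the primary endpoint for the final analysis". None of these places names the test or formula behind the 90%.

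Section 10.2.3.1 makes the primary test a Cox model with treatment arm and age, censored at day 28. Section 10.2.3.5 keeps one interim analysis, at 180 patients, which can stop the trial only for futility (z of 0 or lower).

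Version 2.0, Section 10.2.1, used the same total, mortality rates and alpha and said: "This results in 90% overall power (90% probability to either show efficacy after Stage 1 or Stage 2"). That design had Pocock critical values of 2.176 at both looks and a logistic model. The Version 4.0 history (Appendix 13) records that the stop for efficacy was removed and the power calculation adapted.

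**The concern.** Dropping an efficacy look and lowering the final critical value from 2.176 to 1.96 raises power when everything else is held fixed. If 90% was right for the Version 2.0 design, it should be too low for Version 4.0, yet the number did not move. That suggests a figure copied forward and not recalculated. If so, the protocol would describe the operating characteristics of a design that is no longer being run. A reader might also believe that any shortfall below 360 evaluable patients takes power under 90%, when there is some slack.

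**Working it through.** **Inputs (Version 4.0, Section 10.2.1 and synopsis).** n = 180 per arm, p1 = 0.30, p2 = 0.15, difference d = 0.15, one-sided 2.5%, so z = 1.960. Mean rate = 0.225. Expected deaths = 360 × 0.225 = 81. Under proportional hazards, HR (A to B) = ln 0.85 / ln 0.70 = 0.456.

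**The plan's own 90%, for the Version 2.0 design.** Two stages of 90 per arm, critical value 2.176 at each look, stop at z ≤ 0, equal weights. Power is the chance of crossing at Stage 1 plus the chance of continuing and crossing at the end.

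| Stage-wise mean of z | Stage 1 | Stage 2 | Total |
|---|---|---|---|
| 2.371 (log odds ratio) | 57.7% | 31.3% | 89.1% |
| 2.410 (pooled variance) | 59.2% | 30.8% | 90.0% |
| 2.449 (unpooled variance) | 60.8% | 30.2% | 91.0% |

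Simulation of the logistic Wald test gives 90.2%. The 90% therefore fits Version 2.0.

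**The Version 4.0 design: one final test, 180 per arm.**

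- Pooled z: Φ[(0.15√180 − 1.960√(2 × 0.225 × 0.775)) / √(0.30 × 0.70 + 0.15 × 0.85)] = Φ[(2.0125 − 1.1575) / 0.5809] = Φ(1.472) = 92.9%.
- Unpooled z: Φ(2.0125 / 0.5809 − 1.960) = Φ(1.504) = 93.4%.
- Continuity-corrected z: replace n by 180 × (1 − 1/(180 × 0.15))² = 166.9 in the pooled formula, giving Φ(1.343) = 91.0%.
- Log odds ratio, Wald: 0.8873 / 0.2646 − 1.960 = 1.393, giving 91.8%.
- Fisher's exact test, by enumeration: 91.5%.
- Freedman: 9 × (1 − 0.456)/(1 + 0.456) − 1.960 = 1.406, giving 92.0%.
- Schoenfeld: √(81/4) × 0.786 − 1.960 = 1.577, giving 94.3%.
- Simulated Cox Wald test (20,000 trials, exponential survival, censored at day 28, no age term): 92.8%, or 92.6% when trials with interim z ≤ 0 are counted as failures.

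**Like with like.** With the same formula and the futility stop in both designs, moving from Version 2.0 to Version 4.0 gains 91.6 − 89.1 = 2.5 points (log odds ratio), 93.2 − 91.0 = 2.2 points (unpooled z) or 94.1 − 92.1 = 2.0 points (Schoenfeld).

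**Evaluable patients for exactly 90%.** Pooled z needs 161 per arm (322 in all). The continuity-corrected formula needs 174 per arm (348). The simulated Cox test gives about 90% at 161 per arm. Schoenfeld's formula needs 69 deaths, or about 302 patients, but the simulated Cox test at 151 per arm reaches only about 88%. At an effect this large Schoenfeld's formula is optimistic, so its 94.3% and 302 should not be relied on.

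**The case for a change.** The strongest case for a correction holds the method fixed. Whichever formula is chosen, Version 4.0 has 2.0 to 2.5 points more power than Version 2.0, and Version 2.0 is the design that lands on 90%. The methods that bring Version 4.0 closest to 90% (continuity-corrected z, Fisher, log odds ratio) are not its primary test, which is Cox. Section 10.2.1 and the synopsis paragraph on statistical methods also present the 90% as a computed result, not as a lower bound. Evaluable numbers could fall short of 360 through refused deferred consent, so knowing the slack has some use.

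Most of that stands as a description. The figure was probably carried over, although the history says the calculation was adapted and the documents do not show it, so its origin cannot be settled. It does not show an error that matters. Sample sizes are often planned on a proportions formula even when the analysis is a Cox model. On the continuity-corrected one, 174 per arm rounded up to 180 is an ordinary plan for a nominal 90%. If 91.0% counts as agreeing with 90% for Version 2.0, then 91.0% to 91.8% cannot be called a mismatch for Version 4.0.

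No decision depends on the difference either. The room between 360 and 400 is used for patients randomized in error and for consent withdrawn within 48 hours (Sections 5.1 and 5.2), not when power falls below a target.

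**Conclusion.** No change is needed. On the plan's assumptions (30% against 15%, 360 evaluable patients, one-sided 2.5%), the Version 4.0 design has 91% to 94% power depending on the formula, and about 93% for the Cox test by simulation, net of a futility stop that costs about 0.2 points. The stated 90% is a rounded, conservative figure, 2 to 3 points low for the Cox test. The synopsis statement that the size secures 90% is true under every method tried.

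The simulation assumes proportional hazards with a constant hazard over 28 days and leaves out the age covariate. All figures depend on the assumed mortality rates, which this point does not question. A sponsor revising the text for other reasons could name the method and write that power is at least 90%, but enrolment, the primary test, the futility rule and the conclusions would stay as they are.

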#### 10.2.2. Analysis Sets

**Full analysis set (FAS):** The primary statistical analysis will be based on all randomized patients except patients randomized in error (reason for early termination documented as “Randomized by mistake” in the eCRF) who did not get IMP treatment.

**Safety analysis set (SAF):** Safety analyses will be based on all patients who received at least one infusion of IMP, and patients will be analyzed according to the treatment they actually received.

#### 10.2.3. Statistical Analyses

The SAP will be developed and finalized before the study will be unblinded. The SAP will include the exact definition of endpoints and variables to be analyzed, extensive details on the statistical analysis methods to be used together with the structure of tables and figures to be included as end-of-text tables and figures as well as appended listings for the clinical study report. It will also describe procedures for accounting for missing, unused, and spurious data. This section is a summary of the planned statistical analyses of the primary, secondary, and other endpoints.

Individual data will be listed. Data will be summarized using suitable descriptive statistics; depending on the structure of the data, summary statistics (e.g., number of observations, mean, standard deviation, minimum, median, maximum, lower quartile, upper quartile) or frequency tables may be used.

All data will be displayed by treatment arm if not specified otherwise.

#### **10.2.3.1. Primary Efficacy Analysis**

The primary analysis will be performed based on the FAS.

The primary efficacy variable is 28-day mortality (proportion of patients deceased until day 28). The primary statistical hypotheses to be tested are:

$H_0: HR = 1$

versus

$H_1: HR > 1$

where HR is the hazard ratio derived from the beta coefficient of the primary statistical analysis Cox regression model comparing the SOC + Placebo treatment arm (Arm B) with the SOC + IFX-1 treatment arm (Arm A).

A total of 180 patients are planned to be randomized to Arm A and Arm B using a 1:1 allocation ratio for the first stage. The interim analysis is performed after 180 patients, not counting patients being randomized in error, have been followed-up until day 28 (or died before). In case the interim analysis does not result in an early stop for futility, 180 additional patients are planned to be randomized in a ratio of 1:1 to Arm A and B. The planned maximum number of patients in the study is 360. Depending on the number of patients meeting criteria for additional randomization, more patients will be randomized but not more than 400.

The primary statistical analysis of IFX-1 + SOC compared to SOC alone will make use of a one-sided alpha level of 2.5% and will test for superiority (lower mortality among IFX-1 treated patients). The primary statistical analysis will be based on a Cox proportional hazards regression model with outcome 28-day all-cause mortality as a censored time-to-event variable and explanatory variables treatment arm (Arm B versus Arm A) and age. The primary statistical analysis will be based on all randomized patients except patients randomized in error (reason for early termination documented as “Randomized by mistake” in the eCRF) who did not get IMP treatment.. For the primary analysis, all-cause mortality will be censored at day 28 for subjects who died after day 28 or who have more than 28 days follow-up alive.

The z-statistic for the interim and final analysis will be calculated as the proportion of the beta coefficient for the treatment arm effect and its standard error from the Cox proportional hazards

regression model. The study will be stopped for futility if the z-statistic for the first stage is 0 or lower.

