#### 10.2.3.1. Primary Efficacy Analysis

All efficacy analyses will be performed based on all randomized patients according to the intention-to-treat principle.

The statistical study design of Phase III is a group-sequential adaptive design (two stages) with one interim analysis for stopping for futility or stopping for efficacy. The primary efficacy variable is 28-day mortality (proportion of patients deceased until day 28). The primary statistical hypotheses to be tested are:

$$H_0: p_{IFX-1} = p_{Placebo}$$

versus

$$H_1: p_{IFX-1} < p_{Placebo}$$

where  $p_{IFX-1}$  is the proportion of patients deceased until day 28 in the SOC + IFX-1 treatment arm (Arm A) and  $p_{Placebo}$  is the proportion of patients deceased until day 28 in the SOC + Placebo treatment arm (Arm B).

A total of 180 patients will be randomized to Arm A and Arm B using a 1:1 allocation ratio for the first stage. The interim analysis is performed after all 180 patients have been followed-up until day 28 (or died before). In case the interim analysis does not result in an early stop for efficacy or futility, 180 additional patients will be randomized in a ratio of 1:1 to Arm A and B. The maximum number of patients in the study will not exceed 360.

The group sequential design to show superiority of IFX-1 + SOC compared to SOC alone will make use of a one-sided alpha level of 2.5% and a binding futility stop and will test for superiority (lower mortality among IFX-1 treated patients). The primary statistical analysis will be based on a logistic regression model with outcome 28-day mortality and explanatory variables treatment arm (Arm B versus Arm A), age, sex (male versus female), and  $\text{PaO}_2 / \text{FiO}_2$  at randomization.

The critical values for the interim and the final analysis are derived according to Pocock's design resulting in critical values of 2.176 for both stages. The z-statistic at each stage will be calculated as the proportion of the beta coefficient for the treatment arm effect and its standard error from the logistic regression model. The study will be stopped for futility if the z-statistic for the first stage is 0 or lower.

The z-statistics of the first and the second stage will be combined using the weighted inverse normal combination function ([Bauer and Köhne 1994](#); [Bauer and Köhne 1996](#)). The weights are chosen as  $w_1 = \text{sqrt}(180/360)$  and  $w_2 = \text{sqrt}(1-w_1^2)$ .

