#### **8.2.1. Baseline Assessments (Screening)**

The following procedures will be performed to assess baseline characteristics during screening evaluations and before randomization and IMP administration:

- Check inclusion and exclusion criteria

- Documentation of demographic details (age, gender, race, and ethnicity), medical and COVID-19 history (see Sections 8.2.1.1 and 8.2.1.2). Race information is required for eGFR calculation using the CKD-EPI equation
- 8-point ordinal scale assessment (see Section 8.2.2.2) and oxygenation index ( $\text{PaO}_2 / \text{FiO}_2$ ; one representative measurement within 6h before randomization)
- Documentation of concomitant disease and prior medications (see Sections 8.2.1.3 and 8.2.1.4)
- Baseline safety assessment (height, weight, physical exam, AEs, ECG, urine analysis, pregnancy test, and clinical safety laboratory [including creatinine assessment]); see Section 8.2.3)

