#### 10.2.3.2. Secondary Efficacy Analyses

The secondary efficacy analyses will be performed based on the FAS.

The first secondary efficacy endpoint will only be addressed with statistical hypothesis tests if the primary endpoint is statistically significant using the full overall 2.5% one-sided alpha. If the first secondary endpoint is also statistically significant, the full 2.5% one-sided alpha will be passed to the 4 remaining secondary endpoints. Multiplicity in the secondary endpoints will be addressed with the fallback method. 60-day mortality will be analyzed similar to 28-day mortality and the other secondary endpoints will be evaluated using a logistic regression model with the explanatory variables randomized treatment arm (Arm B versus Arm A) and age for:

1. 60-day all-cause mortality
2. Proportion of patients with an improvement in the provided 8-point ordinal scale at day 15 (at least one score point lower than at randomization)
3. Proportion of patients with an improvement in the provided 8-point ordinal scale at day 28 (at least one score point lower than at randomization)
4. Proportion of patients developing acute kidney failure ( $eGFR < 15 \text{ mL/min}/1.73\text{m}^2$ ) during ICU stay and at day 28
5. Proportion of patients free of any renal replacement therapy within 28 days upon randomization
- 6.

The ordering of the secondary endpoints 2 to 5 for hypothesis testing will be as in above mentioned list. The full 2.5% one-sided alpha for the fallback method will be attributed to the 4 secondary endpoints in the following way 2%, 0.2%, 0.2%, and 0.1%. If the preceding hypothesis test is not significant, subsequent tests will be performed at the aforementioned alpha level. If tests are significant, the alpha is added to the subsequent hypothesis test (e.g., if the primary hypothesis test is significant and secondary endpoints 1-4 are all significant, the fifth secondary endpoint will be tested at an alpha of 2.5%; if the fourth secondary endpoint is not significant, the fifth secondary endpoint will be tested at an alpha of 0.1%).

The primary endpoint as well as all secondary endpoints will also be evaluated as censored time to event variables by Kaplan-Meier type methods. Kaplan-Meier analyses will be performed comparing the two treatment arms overall and within the following stratifications:

- Stratification by site
- Stratification by country

- Stratification by sex
- Stratification by age
- Stratification by comorbidities

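### Version 4.0 mortality and ordinal-improvement models adjust for age only; adding baseline ordinal score and PaO2/FiO2, already collected, would give a small gain in power

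*Combined protocol and SAP*

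**What the plan says.** In Protocol Version 4.0, Section 10.2.3.1, the primary model is a Cox regression "with outcome 28-day all-cause mortality as a censored time-to-event variable and explanatory variables treatment arm (Arm B versus Arm A) and age". Section 10.2.3.2 adds that "60-day mortality will be analyzed similar to 28-day mortality", while the remaining secondary endpoints are "evaluated using a logistic regression model with the explanatory variables randomized treatment arm (Arm B versus Arm A) and age". Two of those are improvement on the 8-point ordinal scale at day 15 and day 28, where improvement means "at least one score point lower than at randomization".

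The screening list in Section 8.2.1 includes "8-point ordinal scale assessment (see Section 8.2.2.2) and oxygenation index", the latter being one PaO2/FiO2 value taken within 6 hours before randomization. Neither variable is a covariate in Sections 10.2.3.1 to 10.2.3.3: those models use age, and the EQ-5D model adds sex. Section 10.2.3.2 also says that "Kaplan-Meier analyses will be performed comparing the two treatment arms overall and within the following stratifications"; the list is site, country, sex, age, comorbidities and standard of care. Section 5.1.1 names no randomization strata.

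The superseded Version 2.0 primary model, for the same ventilated Phase III population, was a "logistic regression model with outcome 28-day mortality and explanatory variables treatment arm (Arm B versus Arm A), age, sex (male versus female"; that sentence goes on to add PaO2/FiO2 at randomization. The difference between versions is not an error. It shows only that the variable was once planned as a covariate here. The separate SAP announced in Section 10.2.3 is not among the documents reviewed and may contain a severity-adjusted sensitivity analysis.

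**The concern.** Baseline respiratory and organ-support severity enters none of the Phase III efficacy analyses that the protocol names, although both measures are already in the database. In Cox and logistic models, leaving out a prognostic covariate pulls the treatment coefficient towards zero and costs some power.

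The ordinal endpoints have a further, structural reason to use the baseline score. Every patient is invasively ventilated at entry (Section 6.2.1), so the starting score can only be 6 or 7 (Appendix 7). A patient at 7 succeeds by reaching 6 while still ventilated; a patient at 6 must come off invasive ventilation. The same binary outcome therefore means different things by starting score. Patients at 7 may also be sicker, which works the other way, so the direction of the gap in improvement rates is uncertain.

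Only efficiency is at stake. Type I error, the stated power and the futility risk are not threatened.

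**Working it through.** **Inputs from Version 4.0.** 28-day mortality 30% versus 15%, one-sided 2.5% (Section 10.2.1); 360 evaluable patients (Synopsis), 180 per arm at 1:1; futility stop if z ≤ 0 after Stage 1 (Section 10.2.3.5); fallback levels 2%, 0.2%, 0.2%, 0.1% for secondary endpoints 2 to 5 (Section 10.2.3.2). Prognostic strengths, the share of patients at score 7 and improvement rates are not in the documents and are assumed.

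**The plan's own figure.**
- Two proportions: SE under H0 = √(2 × 0.225 × 0.775/180) = 0.0440; SE under H1 = √((0.30 × 0.70 + 0.15 × 0.85)/180) = 0.0433; power = Φ((0.15 − 1.96 × 0.0440)/0.0433) = 92.9%. With continuity correction it is 91.0%.
- Log-rank (Freedman): deaths = 180 × 0.30 + 180 × 0.15 = 81; HR = ln 0.70/ln 0.85 = 2.19; z = √81 × (2.19 − 1)/(2.19 + 1) = 3.37; power 92.0%, or 91.8% with the futility stop. Schoenfeld's formula gives 94.3%.

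The stated 90% is met, with some margin, by the age-only plan.

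**Mortality.** Exponential survival calibrated to 30% and 15%, censored at day 28, age HR 1.6 per SD, half the patients at score 7, 6,000 replicates:

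| Assumed HR: PaO2/FiO2 per SD; score 7 vs 6 | Age only | + PaO2/FiO2 + score |
|---|---|---|
| Neither prognostic | 93.8% | 93.6% |
| 1.25; 1.5 | 94.3% | 94.8% |
| 1.4; 2.0 | 94.2% | 95.3% |
| 1.6; 2.5 | 94.2% | 96.3% |
| PaO2/FiO2 pure noise; 2.0 | 94.6% | 95.1% |

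Monte Carlo SE of the differences is 0.1 to 0.2 points. With 30% or 70% at score 7, the 1.4/2.0 case gains 1.0 point each. The gain does not come from a smaller standard error. In the 1.4/2.0 case the mean coefficient moves from 0.817 to 0.847, the mean SE from 0.2385 to 0.2398, and the mean z from 3.40 to 3.51 (+3.2%). Null rejection is 2.3–2.5% age-only and 2.4–2.6% adjusted. At the interim (90 per arm, planned effect), P(z ≤ 0) is 0.5–0.6% age-only and 0.4–0.7% adjusted.

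Separate runs with age HR 1.5 and 3,000 replicates agree: 93.4 to 93.4% with no prognostic value and 93.9 to 95.5% with HRs of 1.3 and 3. If the true effect were only 30% versus 20%, the same two cases give 60.8 to 60.9% and 60.6 to 65.7%. Sixty-day mortality was not simulated separately; the model form is the same.

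**Ordinal improvement.** Let gap = P(improve | 6) − P(improve | 7) on placebo, with p6 = p + gap × share at 7 and p7 = p − gap × (1 − share at 7). Here p = 45% at day 15 and 55% at day 28, with a 15-point benefit, half at score 7 and 8,000 replicates. For example, day 15 with gap +30 points gives p6 = 60% and p7 = 30%.

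Day 15 is tested at 2%. For day 28, "If the preceding hypothesis test is not significant, subsequent tests will be performed at the aforementioned alpha level", so its level is 2% + 0.2% = 2.2% if day 15 succeeds and 0.2% if it fails. The table takes both mortality tests as passed and links the two days by a latent correlation of 0.7.

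| Gap (points) | Day 15 at 2%: age → age + score | Day 28 under the fallback rule |
|---|---|---|
| −30 | 79.4 → 83.6% | 75.1 → 79.8% |
| −20 | 79.4 → 80.9% | 75.2 → 77.0% |
| −10 | 80.2 → 80.4% | 75.3 → 75.4% |
| 0 | 79.5 → 79.5% | 75.1 → 75.3% |
| +10 | 79.4 → 79.7% | 75.5 → 76.2% |
| +20 | 79.1 → 80.4% | 75.9 → 77.8% |
| +30 | 79.4 → 82.9% | 76.0 → 80.2% |

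Monte Carlo SE is 0.1 to 0.4 points, and null rejection at 2% is 2.0–2.4% age-only and 2.1–2.5% adjusted. The gain is nearly the same for either sign of the gap. The 0.2% branch for day 28 is reached in about 20% of trials that pass both mortality tests; within it, power is only 24–26% age-only and 25–29% adjusted.

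**Which sign is plausible?** Suppose 50% of patients at 6 leave ventilation, 30–45% of those at 7 do, and 5–20% of those at 7 sit at 6 still ventilated. The gap then runs from 50 − (45 + 20) = −15 to 50 − (30 + 5) = +15 points, where the day-15 gain is 0.8 and 1.2 points.

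**Mortality against ordinal.** On the z scale, mortality gains 0, 1.2, 3.2 and 6.0% (none, mild, moderate, strong). The ordinal endpoints gain 0, about 0.5, about 2 and about 4.5% at absolute gaps of 0, 10, 20 and 30. A larger gain for the ordinal endpoints is not established.

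**The case against.** Nothing is broken. Age-only adjustment is valid and pre-specified, primary power already exceeds 90%, and the size of any gain rests on prognostic strengths that the documents do not supply. The mortality gain reaches 2 points only in the strongest case.

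The covariates may also be weaker than assumed. Eligibility truncates PaO2/FiO2 to between 60 and 200, Appendix 6 lets it be estimated from saturation, and Section 3.2.4 reports that the Phase II change endpoint depended on positioning. The split between scores 6 and 7 could be lopsided. In runs with a PaO2/FiO2 HR of 1.1 per SD and score HRs of 1.5 to 2.0, with half or 90% at score 7, mortality power changed by −0.2 to +0.5 points. Day-15 ordinal power at an absolute gap of 20, with 10% or 90% at score 7, rose by 0.4 to 1.1 points.

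The reason for dropping PaO2/FiO2 may lie in Version 3.0 or the SAP, neither of which is available. Version 4.0 is dated 12 May 2021, with last follow-up expected in August 2021, so the interim may already have passed.

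Most of this stands as a limit on size and timing. It does not remove the point: the near-zero cases fall at the bottom of the stated range, adding a non-prognostic covariate costs almost nothing, and the change to the two ordinal models does not depend on the interim.

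**Conclusion.** The point holds as an efficiency improvement. The Version 4.0 models for 28-day and 60-day mortality and for ordinal improvement at days 15 and 28 adjust for age only, while two plausible severity measures are collected and left unused.

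The expected gain is about 0 to 2 points of power for 28-day mortality at 30% versus 15%, more if the true effect is smaller (up to about 5 points at 30% versus 20% with strong covariates). For day-15 improvement it is about 0 to 4 points, and for day 28 under the fallback rule 0.1 to 4.7 points. These ranges depend on the assumed prognostic strengths, share at score 7 and improvement rates. The ordinal gains matter only if both mortality tests succeed first. Validity, type I error and the futility risk are essentially unchanged.

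**What to change.** - **Section 10.2.3.2, secondary endpoints 2 and 3:** add baseline ordinal score (6 versus 7) to arm and age. This does not touch the futility rule and can be fixed in the SAP before unblinding.
- **Section 10.2.3.1 and 60-day mortality:** add continuous PaO2/FiO2 at randomization and baseline score to arm and age, provided this is specified before the unblinded interim, because the same model yields the futility z-statistic. If the interim has already taken place, keep the age-only primary model and report the severity-adjusted Cox model as a pre-specified sensitivity analysis.
- **Missing covariates:** state a blinded rule so that no patient in the full analysis set is dropped, for example the pooled mean for PaO2/FiO2 and the most frequent value for the score. Few gaps are expected: PaO2/FiO2 is an eligibility criterion, and the score is needed to derive endpoints 2 and 3.
- **Sensitivity:** keep the age-only models wherever the adjusted model becomes the main one.

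No new data are needed. About 81 deaths at the final analysis and about 40 at the interim support four model terms (roughly 20 and 10 per term). The costs are a further amendment for the primary model, following the scientific advice behind Version 4.0, and hazard and odds ratios that are conditional on severity and so not directly comparable with the age-only ones.
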